1.5.5.10 Portal Vein Thrombosis

Transplanted islets release tissue factor and exhibit prothrombotic properties when infused to an intravascular site such as the portal vein¹²⁵. A partial portal vein thrombosis has been reported in one of six subjects transplanted at the intramural National Institutes of Health (NIH) program²⁵. In the Edmonton single-center experience, the risk of partial portal vein thrombosis was 3% in more than 100 intraportal islet transplants¹¹³. The management of partial vein thrombosis includes anticoagulation therapy which may lead to intra-abdominal hemorrhage requiring transfusion and/or surgical intervention^{125, 126}. There is one published report of complete thrombosis of the portal vein after transplantation of partially purified pancreatic islets in a combined islet/liver allograft, which necessitated emergency re-transplantation of the liver^{126, 127}. This complication probably related to the transplantation of partially purified islet tissue derived from 4 donors into a freshly transplanted liver. A right upper quadrant ultrasound including Doppler examination of the portal vein was performed on islet transplant recipients on days 1 and 7 post transplant. Early diagnosis and prompt management of branch vein portal occlusion with systemic heparinization may prevent clot propagation. Repeated intraportal islet transplants are generally contraindicated in subjects who have experienced prior portal thrombosis.

1.5.5.11 Injuries to Other Structures

One instance of gall bladder perforation during percutaneous transhepatic catheterization of the portal vein requiring laparoscopic cholecystectomy has been reported to the International Islet Transplant Registry¹⁰⁸. Acute cholecystitis, possibly related to percutaneous transhepatic catheterization of the portal vein, has been noted in 2 of the 86 islet allograft recipients reported to CITR¹¹⁵. Gall bladder hematoma (n=1) and gall bladder opacification (n=2) have been observed as well.

1.5.5.12 Risk of Auxiliary Graft Biopsy

This biopsy is a minor procedure that will be done under direct visualization under local anesthesia. The main risks associated with this are superficial infection and bleeding.

1.5.6 Procedures for Minimizing Risks

A number of features of the proposal have been designed to maximize the safety of subjects in the trial. Important selection criteria include avoidance of any medical condition that might significantly increase the risk related to islet transplantation. Importantly this includes selection of kidney recipients who have stable graft function and who are at a low risk for rejection of their graft. In addition, renal graft function in potential trial subjects has to be sufficient (CrCl of > 40 mL/min) so that it is unlikely that they will experience imminent graft failure and face the need for ongoing immunosuppression for an islet graft in the absence of a functioning kidney.

To ensure further that there is no detrimental impact on renal graft function, the maintenance immunosuppression regimen already in place for the renal graft will be continued without marked changes to benefit the islet transplant. This approach will avoid immunosuppressant drug changes that

could potentially precipitate renal allograft rejection.

In addition, the induction immunosuppression regimen based on rabbit ATG is well studied and has been demonstrated to have a favorable safety profile in solid organ transplantation. The islet preparation to be infused will be isolated from cadaveric donors thoroughly tested for transmissible infectious agents and will be free of recent high-risk behaviors. In addition, the islet product will be tested preinfusion to verify a suitable level of purity, viability, mass, and endotoxin.

Since gaining insulin independence is dependent on the recovery and infusion of a sufficient islet mass per recipient BW, the trial has been limited subjects < 100 kg in an attempt to maximize the likelihood that insulin independence will be achieved with one (or two) islet transplants. It is recognized that subjects ≥ 100 kg should benefit equally for this therapy should a sufficient islet mass be obtainable.

The informed consent process is carefully organized to minimize unrealistic expectations. We will also reject volunteer subjects who are so desperate as to be incapable of understanding and/or coping with the possibility of failure. We believe that our process leading to informed consent is purposefully organized so as to minimize psychological risk to the recipient.

1.5.7 Benefits of Allogeneic Islet Transplantation

The benefits of islet transplantation include improved glycemic control in subjects who have been unable to achieve an HbA1c of less than 7.0% after a dedicated trial (> 4 months) of diabetes management by an experienced diabetologist. Transplantation should also benefit subjects who are well-controlled but have multiple episodes of hypoglycemia.

Of note, there is a growing recognition that a partially functioning islet graft in conjunction with low doses of insulin may also reduce or eliminate hypoglycemic events and improve glucose control¹²⁸⁻¹³⁰. In addition, experimental evidence suggests that even with partial graft function, providing endogenously produced c-peptide may contribute to restoration of physiological function.

2. OBJECTIVES

2.1 Primary Objective

The primary objective is to test the hypothesis that AAT treatment during the period of islet engraftment will increase the functional engrafted islet mass and that this will increase insulin independence rates at day 75, and secondarily would improve the long-term durability of islet function.

2.2 Secondary Objectives

Secondary objectives of this study will assess whether AAT treatment compared to control therapy at the time of islet transplantation, improves metabolic control and reduces the risk of cardiovascular and renal complications from diabetes. Mechanistic studies will probe the mechanism of action of AAT on recipient PBL and their correlation with success at the primary end-point and engrafted mass.

3. SELECTION AND WITHDRAWAL OF SUBJECTS

3.1 Inclusion Criteria

Subjects who meet *all* of the following criteria are eligible:

1. Male and female subjects age 18 to 70 years.
2. Subjects who are able to provide written informed consent and to comply with the procedures of the study protocol.
3. Subjects in the United States must have one of the following payment mechanisms in place:
 - a. Medicare,
 - b. A third-party insurer who agrees, via pre-authorization, to pay for participation in the study, or
 - c. Another mechanism of payment (self-pay, hospital, university, donations, etc.) for participation in the study.
4. Clinical history compatible with T1D with disease onset < 40 years of age and insulin-dependence for ≥ 5 years at the time of enrollment.
5. Absent stimulated c-peptide (< 0.3 ng/mL) in response to a MMTT [Boost[®] 6 mL/kg body weight (BW) to a maximum of 360 mL; another product with equivalent caloric and nutrient content may be substituted for Boost[®]] measured at 60 and 90 min after start of consumption.
6. Subjects who are ≥ 3 months post-renal transplant who are taking appropriate calcineurin inhibitor (CNI) based maintenance immunosuppression ([tacrolimus alone or in conjunction with sirolimus, mycophenolate mofetil, myfortic, or azathioprine; or cyclosporine in conjunction with sirolimus, mycophenolate mofetil, or myfortic] \pm Prednisone ≤ 10 mg/day).
7. Stable renal function as defined by a creatinine of no more than one third greater than the average creatinine determination performed in the 3 previous months prior to islet transplantation, until rejection, obstruction or infection is ruled out.
8. Subjects who meet one of the options in the following criterion are eligible for transplantation:
 - Reduced awareness of hypoglycemia manifested by a Clarke score of 4 or more measured upon study enrollment and at least one episode of severe hypoglycemia in the 12 months prior to study enrollment.

OR

 - a subject must have a reduced awareness of hypoglycemia manifested by a Clarke score of 4 or more and at least 1 episode of severe hypoglycemia;

OR

 - Any subject not meeting the hypoglycemia option must have an HbA1c $\geq 7.5\%$.

3.2 Exclusion Criteria

Subjects who meet *any* of these criteria are *not* eligible:

1. Weight more than 90 kg or body mass index (BMI) > 30 kg/m².
2. Insulin requirement of >1.0 IU/kg/day or <15 U/day.
3. Other (non-kidney) organ transplants except prior failed pancreatic graft where graft failure is attributed to thrombosis within the first 4 weeks or to other technical reasons that require graft pancreatectomy; with the graft pancreatectomy occurring more than 6 months ago.
4. Untreated or unstable proliferative diabetic retinopathy.
5. Blood Pressure: SBP > 160 mmHg or DBP >100 mmHg despite treatment with antihypertensive agents.
6. Calculated GFR of ≤ 40 mL/min/1.73 m² using the subject's measured serum creatinine and the Chronic Kidney Disease Epidemiology Collaboration (CKD-EPI) equation [1]. Strict vegetarians (vegans) will be excluded only if their estimated GFR is ≤35 mL/min/1.73 m².
7. Proteinuria (albumin/creatinine ratio or ACr > 300mg/g) of new onset since kidney transplantation.
8. Calculated panel-reactive anti-HLA antibodies > 50%. Subjects with calculated panel reactive anti-HLA antibodies ≤ 50% will be excluded if any of the following are detected:
 - Positive cross-match,
 - Islet donor-directed anti-HLA antibodies detected by Luminex Single Antigen/specificity bead assay including weakly reactive antibodies that would not be detected by a flow cross-match, or
 - Antibodies to the renal donor (i.e. presumed *de novo*).
9. For female subjects: Positive pregnancy test, presently breast-feeding, or unwillingness to use effective contraceptive measures for the duration of the study and 4 months after discontinuation. For male subjects: intent to procreate during the duration of the study or within 4 months after discontinuation or unwillingness to use effective measures of contraception. Oral contraceptives, Norplant®, Depo-Provera®, and barrier devices with spermicide are acceptable contraceptive methods; condoms used alone are not acceptable.
10. Presence or history of active infection including hepatitis B, hepatitis C, HIV, or tuberculosis (TB). Subjects with laboratory evidence of active infection are excluded even in the absence of clinical evidence of active infection.
11. Negative screen for Epstein-Barr virus (EBV) by IgG determination at time of screening or previous kidney transplant.
12. Invasive aspergillus, histoplasmosis, and coccidioidomycosis infection within the last year.
13. Any history of malignancy except for completely resected squamous or basal cell carcinoma of the skin or other cancers for which the patient is at least 5 years post curative therapy where a very high likelihood (>99%) that cure has been achieved, such as in certain types of low grade thyroid cancer or early stage breast cancer.

14. Known active alcohol or substance abuse.
15. Evidence of Factor V Leiden mutation or other laboratory evidence of hypercoagulable state.
16. Any coagulopathy or medical condition requiring long-term anticoagulant therapy (e.g. warfarin) after islet transplantation (low-dose aspirin treatment [325 mg PO] is allowed) or subjects with international normalized ratio (INR) > 1.5. The use of Plavix is allowed only in conjunction with mini- laparotomy procedure at the time of islet transplant.
17. Severe co-existing cardiac disease, characterized by any one of these conditions:
 - Recent MI (within past 6 months);
 - Evidence of ischemia on functional cardiac exam within the last year;
 - Left ventricular ejection fraction < 30%; or
 - Valvular disease requiring replacement with prosthetic valve.
18. Persistent serum glutamic-oxaloacetic transaminase (SGOT [AST]), serum glutamate pyruvate transaminase (SGPT [ALT],) alkaline phosphatase or total bilirubin, with values > 1.5 times normal upper limits will exclude a subject.
19. Active infections (except mild skin and nail fungal infections).
20. Active pancreatitis.
21. Active peptic ulcer disease, symptomatic gallstones, or portal hypertension.
22. Use of any investigational agents within 4 weeks of enrollment.
23. Administration of live attenuated vaccine(s) within 2 months of enrollment.
24. Any medical condition that, in the opinion of the investigator, will interfere with the safe participation in the trial. (Cancer screenings should be performed per current American Cancer Society guidelines).
25. Positive screen for BK virus by polymerase chain reaction (PCR) performed at time of screening.
26. A kidney transplant patient with type 1 diabetes who has an HbA1c < 7.5 and no history of severe hypoglycemia.
27. Selective or severe IgA deficiency (levels < 5-7 mg/dL)
28. AAT deficiency (defined as plasma level of AAT < 8 μ M-50 mg/dL)

4. STUDY DESIGN

The study will be a prospective, multi-center clinical trial in kidney transplant recipients with T1D, assessing the effect of AAT on islet transplant engraftment and durability of function. Subjects considered for enrollment will be: 1) at least 3 months post-renal transplant, 2) have stable renal graft function and calculated GFR by measured SCr and the CKD-EPI equation, 3) be free of renal rejection episodes for \geq 3 months, and 4) receive standard of care diabetes management either prior to enrollment or during the study.

If subjects have not received appropriate diabetes management in the 12 months prior to enrollment, they must undergo a period of standardized diabetes care by an experienced clinician at the transplant center using the current ADA's standards of medical care in diabetes. After at least 4 months of structured care by an experienced diabetologist, subjects with a Clarke score of 4 or more and at least one episode of severe hypoglycemia will be consented and listed for islet transplantation. If after 12 months subjects do not achieve acceptable glycemic control ($\text{HbA1c} \geq 7.5\%$), they will be consented and listed for islet transplantation. If after 12 months a subject has either a severe hypoglycemic event and Clarke score of 4 or more, or an $\text{HbA1c} \geq 7.5\%$, the subject will be eligible for islet transplantation.

Subjects may undergo a period of standardized diabetes care by an experienced diabetologist. These subjects will be treated by diabetes management following current ADA guidelines for glycemic control. Similar guidelines for insulin therapy will also be applied to subjects with partial function following islet transplantation. This will include a target HbA1c of $< 7.5\%$, fasting glucose level of $< 140 \text{ mg/dL}$ and 2-hour postprandial glucose levels of $< 180 \text{ mg/dL}$. Target levels can be adjusted as needed based on the development of hypoglycemic episodes. Subjects will be expected to perform self BG monitoring at least 4 times/day and to utilize an insulin regimen consisting of at least 3 insulin injections/day (the type of insulin used should be tailored to the individual subject and include currently available insulin analogs). Insulin pump therapy is not prohibited nor is it required, but may be recommended by the treating diabetologist.

Clinical evaluations should occur quarterly, with additional diabetes education or nutrition visits (including education in carbohydrate counting) as necessary. Initially, more frequent appointments may be required to convert subjects to a more intensive insulin regimen. The insulin dose needed will be adjusted to obtain and sustain target glucose and HbA1c .

Hypoglycemic events that occur within 28 days after an islet transplant will not be considered as severe hypoglycemic events if the subject is receiving insulin therapy at that time.

When a suitable islet preparation becomes available, a subject having a blood type compatible with the islet donor and who is crossmatch negative will be selected from the active wait list.

[figure not shown]
After preliminary testing, a subject will be invited to the hospital for transplantation upon determination of preliminary islet suitability based on count, quality, ABO and negative serum crossmatch. The subject will begin the planned induction therapy and Solumedrol premedication. These drugs can be administered via central vein catheter, peripherally inserted central catheter (PICC) line, or peripheral IV⁹⁸.

A period of in vitro culture is considered essential to the protocol because the use of rabbit ATG induction immunosuppression may cause a transient cytokine release associated with the initial doses. The period of in vitro culture after treatment with rabbit ATG will allow any cytokine release to dissipate. The culture period will also permit microbiological and potency assessment of the islet preparation prior to transplant.

At the end of the culture period after the islets have been inspected, the intended recipient will receive

GLASSIA, administered preoperatively at a dose of 90 mg/kg at a rate of 0.14 ml/minute and if tolerated without evidence of hypersensitivity, the rate will be increased to 0.2ml/min. Subsequent doses (30 mg/kg) will be administered during the engraftment period, three times a week over the first three weeks.

Figure 1. Timeline for Enrollment and Transplantation

Following induction therapy, subjects will remain on a calcineurin-based maintenance immunosuppression regimen. This can consist of tacrolimus alone or in conjunction with sirolimus, mycophenolate mofetil, myfortic, or azathioprine; or cyclosporine in conjunction with sirolimus, mycophenolate mofetil, or myfortic. Subjects on CsA alone will be excluded. Up to 10 mg/day of steroids are also acceptable in conjunction with either regimen. Mycophenolate sodium is an acceptable alternative to mycophenolate mofetil. Drug target levels can be adjusted at the discretion of the treating transplant physician based on subject care needs including islet graft rejection, drug-related islet graft injury, drug-related side effects, or infection.

[figure not shown]
If possible, islet transplant procedure will be performed by open mini-laparotomy approach to facilitate implantation of an auxiliary graft in the subcutaneous space. If the open approach is not safe, the percutaneous approach is acceptable and the auxiliary graft will be transplanted by a small incision under local anesthesia. Each approach is capable of gaining access to the portal system and there is no evidence to suggest that the choice of approach will impact the function of the transplanted islets. Islets may be infused together with heparin according to the section entitled "Heparin". Following completion of heparin, subjects will be treated with enoxaparin/dalteparin, aspirin, and pentoxifylline according to section entitled "Anticoagulation Prophylaxis / Hematological Agents".

Following transplant, subjects will receive prophylactic antibiotics according to section entitled

"Antibacterial, Antifungal, and Antiviral Prophylaxis". Optimal glycemic control will be achieved according to section entitled "Updated Vaccinations". Subjects will remain up to date on CDC-recommended adult vaccinations; please refer to the MOP for guidance.

Islets will be administered with the goal of achieving insulin independence as defined below and administering a total of >5,000 IEq/kg recipient BW for the first transplant, and $\geq 4,000$ IEq/kg recipient BW for subsequent transplants. It is expected that achieving insulin independence will potentially require more than one islet transplant. Islet transplants will be administered at least 30 days apart and it is recommended that subsequent transplants occur within six months of the preceding transplant. Subjects who have completed 8 months follow- up after their initial transplant will no longer be eligible for additional islet transplants under this protocol. It is recognized that availability of suitable donor pancreata may affect the interval between transplants.

Figure 2. Timing of First IAK Transplant and Immunosuppression Regimen

Centers are encouraged to re-infuse subjects with partial graft function with the goal of gaining a state fully independent of exogenous insulin administration. The pancreatic islet product is obtained by purification of islets of Langerhans from suitable deceased donor pancreata. One batch comprises purified pancreatic islets obtained from one donor pancreas, and processed during a single purification run.

Subjects can receive a maximum of 3 allogeneic donor islet infusions for the duration of the study.

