1.5.2 Risks of Use of Investigational Agent: GLASSIA

GLASSIA is human alpha1 proteinase inhibitor indicated in patients with lung disease secondary to severe hereditary deficiency of alpha1-antitrypsin (AAT). For this purpose the recommended dose for chronic therapy is 60 mg/kg once weekly at a rate of 0.2 ml/kg-bw/min via iv infusion. For this study we will be dosing at 30 mg/kg per dose. Its use is contraindicated in patients with IgA deficiency with anti-IgA antibodies as this may result in severe hypersensitivity and or anaphylaxis. GLASSIA is pregnancy category C.

Since GLASSIA is product purified from human plasma, there is a theoretical risk of transmitting infectious agents such as viruses, including CJ virus. However, no seroconversions for hepatitis (HBV and HCV), HIV or other known infectious agents have been reported in clinical studies with GLASSIA.

Common adverse reactions $\geq 5\%$ include: headache, musculoskeletal discomfort, vessel puncture site bruise, Headache, reaction at the injection site such as redness, rash, swelling, itching, nausea, and rhinorrhea.

Adverse reactions occurring at >0.5% noted in the package insert include: pharyngitis (1.2%), headache (0.8%) and cough (0.5%).

Rare but serious reactions include: increased clotting in the blood and viral infection.

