5.1 Investigational Agent: GLASSIA

GLASSIA is human alpha1 proteinase inhibitor indicated in patients with lung disease secondary to severe hereditary deficiency of alpha1-antitrypsin (AAT). For this purpose the recommended dose for chronic therapy is 30 mg/kg once weekly at a rate of 0.2 ml/kg/min via iv infusion. In the current trial, patients will receive a 90 mg/kg load followed by 30mg/kg 3x/week for 3 weeks. It should take approximately 30 minutes to infuse. Its use is contraindicated in patients with IgA deficiency with anti-IgA antibodies as this may result in severe hypersensitivity and or anaphylaxis. GLASSIA is pregnancy category C.

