5.1.1 Formulation, Dosing, Administration and Emergency Precautions

GLASSIA (Kamada) is available commercially as a ready to use, liquid preparation of purified human-alpha₁-protease inhibitor (Alpha₁-PI). It is prepared from human plasma though cold ethanol fractionation. GLASSIA is available in with UPS Water for Injection (to 1 gm/50ml).

The first dose of GLASSIA will be calculated with the recipients body weight recorded during the admission for transplant. Subsequent doses will be calculated using the weight recorded on the admission for that dosing. The dose will be rounded to the nearest whole vial dose but must be within

10% of calculated dose. Patients will receive a loading dose of 90 mg/kg followed by maintenance dose of 30mg/kg/dose. A trough level will be measured between 2nd and 3rd dose. If the AAT level is not between 2.5-3.5 mg/ml we will increase dose to 60mg/kg/dose for the remaining doses.

GLASSIA will be used within three hours per package insert guidelines. The infusion will be administered by a qualified individual, using a 5 micron in-line filter during the infusion. Vital signs will be recorded within 30 minutes before initiating the infusion and every 30 minutes during the infusion and within 15 minutes after completing the infusion.

With each infusion, medical personnel will be available to treat subjects who experience anaphylaxis. Emergency treatment such as 0.3 mL to 0.5 mL aqueous epinephrine (1:1000 dilution) subcutaneously and other resuscitative measures including oxygen, IV fluids, antihistamines, corticosteroids, pressor amines, and airway management, as clinically indicated, should be provided.

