7.4 Islet Transplant and Study Treatment Visits

Blood group compatible and crossmatch negative subjects selected for islet transplantation will be invited to the study center upon determination of preliminary islet suitability based on count and quality. After preliminary testing detailed in Appendix 1, SOE (- 2 days relative to transplant), the subject will be admitted for induction therapy with rabbit ATG. This can be administered via central vein catheter, PICC line, or peripheral IV⁹⁸. A period of in vitro culture is considered essential to the protocol because of the use of rabbit ATG induction

Immunosuppression may cause a transient cytokine release associated with the initial doses. The period of in vitro culture will allow time for any cytokine release to dissipate after treatment of the subject with ATG and will also permit time for microbiological and potency assessment of the islet preparation prior to transplant.

Once islets have been examined at the end of the culture period but prior to final release testing, the pharmacy will compile the needed dose to allow the infusion to be completed within three hours of reconstitution. GLASSIA will be infused within three hours before the intended start of the islet infusion but after the final release criteria confirm islet suitability.

Following induction therapy, subjects will remain on a calcineurin-based maintenance immunosuppression regimen. This can consist of tacrolimus alone or in conjunction with sirolimus, mycophenolate mofetil, myfortic, or azathioprine; or cyclosporine in conjunction with sirolimus,

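### Section 4 gives the GLASSIA infusion rate without its per-kilogram term, so the 90 mg/kg load would take more than a day at 70 kg instead of about 30 minutes

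*Combined protocol and SAP*

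**What the plan says.** Section 4 (Study Design) sets the pre-transplant load at 90 mg/kg, given "at a rate of 0.14 ml/minute and if tolerated without evidence of hypersensitivity, the rate will be increased to 0.2ml/min". This is the only rate stated for the trial's own infusions. Section 5.1.1 gives the product strength as 1 g in 50 ml but no rate.

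Other sections constrain the timing:

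- Section 5.1, after naming the 90 mg/kg load and the 30 mg/kg maintenance doses: "It should take approximately 30 minutes to infuse".
- Section 5.1.1: "GLASSIA will be used within three hours per package insert guidelines".
- Section 7.4: "the pharmacy will compile the needed dose to allow the infusion to be completed within three hours of reconstitution".
- Section 7.4 again: "GLASSIA will be infused within three hours before the intended start of the islet infusion", and only once final release testing has confirmed the islets are suitable.

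A per-kilogram rate appears twice, both times for the labelled chronic use rather than for this trial. Section 1.5.2 says "the recommended dose for chronic therapy is 60 mg/kg once weekly at a rate of 0.2 ml/kg-bw/min via iv infusion", and Section 5.1 says "the recommended dose for chronic therapy is 30 mg/kg once weekly at a rate of 0.2 ml/kg/min via iv infusion".

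**The concern.** The two figures in Section 4 are plain millilitres per minute. For a dose prescribed by body weight at 20 mg/ml, that is far too slow to agree with a half-hour infusion or a three-hour limit. The load is the time-critical dose: it must fit between islet release and islet infusion.

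If the sentence is wrong, sites hold an administration instruction for the investigational agent that they cannot follow. The realistic results are a query to the coordinating center, a rate settled site by site, or, less plausibly, a delayed or incomplete load. Over-rapid infusion is not what the literal text directs, because the error runs in the slow direction.

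**Working it through.** **Inputs**

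- Load 90 mg/kg; rate 0.14 then 0.2 ml/min (Section 4).
- Strength 1 g/50 ml = 1000/50 = 20 mg/ml (Section 5.1.1).
- Maintenance dose 30 mg/kg, rising to 60 mg/kg if the trough is off target (Section 5.1.1).
- Upper weight limit 90 kg (Section 3.2 excludes "Weight more than 90 kg"). Weights of 50 and 70 kg are my assumptions.

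**Can the stated 30 minutes be reproduced?** Volume per kg = 90/20 = 4.5 ml/kg. Time = volume/rate.

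Rate as written:

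| Weight | Load volume | Time at 0.14 ml/min | Time at 0.2 ml/min |
|---|---|---|---|
| 50 kg | 225 ml | 26.8 h | 18.8 h |
| 70 kg | 315 ml | 315/0.14 = 2250 min = 37.5 h | 315/0.2 = 1575 min = 26.3 h |
| 90 kg | 405 ml | 48.2 h | 33.8 h |

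It cannot. At 70 kg even the faster rate is 1575/30 = 52.5 times too slow.

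Rate read per kilogram (body weight cancels):

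- 4.5/0.14 = 32.1 min.
- 4.5/0.2 = 22.5 min.
- Stepping up after 15 minutes (my assumption): 15 + (4.5 − 15 × 0.14)/0.2 = 27 min.

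These agree with the stated half hour and meet every three-hour limit.

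**What the written rate delivers in three hours**

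- At 0.14 ml/min: 0.14 × 180 = 25.2 ml = 504 mg.
- At 0.2 ml/min: 0.2 × 180 = 36 ml = 720 mg.
- The 70 kg load is 6300 mg, so 8.0% to 11.4% would be given.
- At 50 kg (4500 mg) the range is 11.2% to 16.0%; at 90 kg (8100 mg) it is 6.2% to 8.9%.

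**Does any allowance rescue it?**

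- Weight: at 0.2 ml/min the load fits in three hours only up to 36/4.5 = 8 kg.
- Vial rounding: taking the full 10% tolerance downward still leaves 0.9 × 26.25 = 23.6 h at 70 kg.
- A different dose: Section 4 attaches the rate to the load. If it were carried over to a 30 mg/kg dose (1.5 ml/kg, 105 ml at 70 kg), that dose would take 105/0.2 = 525 min = 8.75 h, still well past three hours.

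**Maintenance doses at the per-kilogram rate**

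- 30 mg/kg: 1.5/0.2 = 7.5 min to 1.5/0.14 = 10.7 min.
- 60 mg/kg (3.0 ml/kg): 3.0/0.2 = 15.0 min to 3.0/0.14 = 21.4 min.

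**The case against.** The best defence is that the protocol, read as a whole, nearly corrects itself. Section 5 is the treatment section. Section 5.1 prints the per-kilogram maximum, then the trial doses, then a duration that only a per-kilogram rate can approach, and Section 1.5.2 repeats the unit. A literal reading implies a day-long infusion inside a three-hour window, so whoever programs the pump would almost certainly notice. On that view a site query is realistic and a grossly incomplete load is not.

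Much of this stands. An 8% load measures the inconsistency; it does not predict what sites would do. Section 5.1 also does not say which dose its half hour describes.

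Two things survive. The per-kilogram figures elsewhere belong to labelled chronic therapy, so they do not set the trial's rate. The 0.14 starting step appears only in Section 4. A site that fell back on Section 5.1 would find only the higher rate and could skip the slower start that Section 4 uses to watch for hypersensitivity. The three-hour conflict holds whichever dose the half hour refers to. Nor does this look like a text-extraction fault: the term is missing from two differently written units, with no gap or redaction mark.

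**Conclusion.** The concern holds. The Section 4 rate is wrong as written and cannot be followed at any adult weight: 26.3 to 37.5 hours for the load at 70 kg, and 18.8 to 48.2 hours across 50 to 90 kg, against about 30 minutes expected and three hours allowed. The 50 and 70 kg weights are assumed, and the conclusion does not depend on them.

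A dropped per-kilogram term is the probable cause, because restoring it gives 22.5 to 32.1 minutes and removes every conflict. That remains an inference until checked against the labelling, which these documents do not include.

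The point is confined to drug administration. The mg/kg dose, primary endpoint, power and analysis are unaffected. It should be corrected because it is an operative instruction for the agent under test in a multi-center trial.

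**What to change.** In Section 4, change the rate to 0.14 ml/kg/min rising to 0.2 ml/kg/min, after confirming it against the product labelling, and repeat it in Section 5.1.1, where sites will look for administration details.

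Two optional editorial points carry no weight in this finding. Section 5.1 could say that the half hour refers to the 90 mg/kg load, since 30 and 60 mg/kg doses would take about 8 to 11 and 15 to 21 minutes. The labelled chronic dose, 60 mg/kg weekly in Section 1.5.2 but 30 mg/kg weekly in Section 5.1, should be reconciled against the labelling; this does not change the study dose.

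The cost is one unit correction and a sentence or two, with no change to design or analysis.
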